Table 2:	Study Drug Kits and Treatments, Study OS440-3005.....	22
Table 3:	Taper and Washout Periods for Specific Anti-spasticity and/or Muscle Relaxation Medications, Study OS440-3005	26
Table 4:	Clinical Laboratory Tests, Study OS440-3005.....	31

[figure not shown]
List of In-Text Figures

Figure 1:	Timeline Diagram, Study OS440-3005.....	16
Figure 2:	Flowchart of Open-Label Dosing Regimen, Study OS440-3005.....	25

List of Abbreviations and Definitions of Terms

Abbreviation	Definition
AE	Adverse event
AERT	Arbaclofen extended-release tablets
ALT	Alanine transaminase
AST	Aspartate transaminase
BID	Twice daily
BP	Blood pressure
BUN	Blood urea nitrogen
CFR	Code of Federal Regulations
CNS	Central nervous system
CRO	Contract Research Organization
C-SSRS	Columbia–Suicide Severity Rating Scale
DSMB	Data Safety Monitoring Board
DSS	Disability Status Scale
ECG	Electrocardiogram
eCRF	Electronic case report form
EDSS	Expanded Disability Status Scale
FDA	Food and Drug Administration
FS	Functional system
GCP	Good Clinical Practices
GFR	Glomerular filtration rate
IB	Investigator’s Brochure
ICF	Informed Consent Form
ICH	International Conference on Harmonization
IEC	Independent Ethics Committee
IND	Investigational New Drug
IRB	Institutional Review Board
LUTS	Lower urinary tract symptoms
mAS	Modified Ashworth Scale
MDRD	Modification of Diet in Renal Disease Study
MedDRA	Medical Dictionary for Regulatory Activities
MS	Multiple sclerosis
NARCOMS	North American Research Committee on MS
NIMH	National Institute of Mental Health
PGIC	Patient Global Impression of Change
PT	Preferred term
RBC	Red blood cell
RDC	Remote data capture
ROM	Range of movement
RR	Relapsing-remitting (MS)
SAE	Serious adverse event
SAP	Statistical Analysis Plan
SD	Standard deviation
SOC	System organ class
SP	Secondary-progressive (MS)
TEAE	Treatment-emergent adverse event
TNmAS-MAL	Total Numeric-transformed mAS score of the most affected limb
US	United States
USP	Urinary Symptom Profile – USP® questionnaire
WBC	White blood cell
WHO	World Health Organization

1 STUDY ADMINISTRATIVE STRUCTURE

2 INTRODUCTION

2.1 Multiple Sclerosis and Spasticity

Multiple sclerosis (MS) is an acquired inflammatory demyelinating disease of the central nervous system (CNS) that is regarded as the foremost cause of non-traumatic neurologic disability in adults in North America. Multiple sclerosis has a prevalence of approximately 1 case per 1,000 in the population and a predominance in women (female to male ratio, 2:1). The mean age at onset is 30 years. Although MS is a heterogeneous illness, in 85% of patients it begins with episodic, largely reversible neurologic dysfunction, in a pattern termed relapsing-remitting (RR) MS. In 75% of those patients, the disease advances over time to a steady, irreversible worsening state designated secondary-progressive (SP) MS. Less than 5% of patients have very severe disability (fulminant MS) within the first 5 years after onset, and 10% to 20% of patients remain unimpaired without therapy (benign MS) for 20 years or so.

Clinical manifestations of MS include visual loss, paresthesias, weakness, spasticity, fatigue, and pain. Multiple sclerosis symptoms may initially wax and wane with the onset and resolution of exacerbations. However, in the latter disease stages, most patients progress to have some permanent disability. Multiple sclerosis treatment relies on pharmaceutical agents to slow disease progression and reduce the burden of MS symptoms.

Spasticity is a common complication in MS and occurs in up to 84% of patients. The main sign of spasticity is resistance to passive limb movement characterized by increased resistance to stretching, clonus, and exaggerated deep reflexes. The associated features of spasticity, including pain, gait disorders, fatigue, and loss of function, significantly affect patient quality of life. Data collected from the North American Research Committee on MS (NARCOMS) Patient Registry showed that 34% of over 20,000 MS patients surveyed experienced moderate, severe, or total limitation of physical abilities due to spasticity. Consequently, one of the main objectives for the functional management of MS is the symptomatic treatment of spasticity, aiming to improve gait, hygiene, and all the impeded activities of daily living. However, current oral pharmacologic treatments of MS fail in the total control of this problem, both for intolerability or lack of efficacy, defining the unmet medical need for treatment of spasticity.

Baclofen has been in clinical use for more than 35 years and the benefits and risks are well characterized. It is approved for the treatment of spasticity due to MS and spinal cord injury and is a first-line pharmacotherapy as described in the MS Council for Clinical Practice Guidelines for treatment of spasticity in MS. However, the therapeutic potential of baclofen is limited because it is poorly tolerated by patients due to the side effects of sedation, drowsiness, and worsening of fatigue. Therefore, an unmet medical need exists for an effective, better tolerated oral treatment of spasticity.

Baclofen is a racemate (rac-baclofen) consisting of an equal mixture of two enantiomers: the l- or R-enantiomer (arbaclofen) and the d- or S-enantiomer.

Osmotica Pharmaceutical is currently developing arbaclofen extended-release tablets (AERT) for the treatment of spasticity in patients with MS. Arbaclofen is the active R-enantiomer of baclofen and it has been postulated that the efficacy of baclofen is primarily due to the R-enantiomer. This

clinical study is an open-label extension of the Phase 3 double-blind Study OS440-3004 to evaluate the long-term safety and tolerability of AERT in patients with spasticity due to MS.

3 STUDY OBJECTIVES

3.1 Primary Objective

The primary objective of this study is to evaluate the long-term safety and tolerability of AERT in patients with spasticity due to MS.

3.2 Secondary Objectives

The secondary objectives are to:

- Assess the Patient Global Impression of Change (PGIC) over 1 year.
- Assess the Total Numeric-transformed modified Ashworth Scale score of the most affected limb (TNmAS-MAL) over 1 year.
- Assess the Expanded Disability Status Scale (EDSS) over 1 year.

4 INVESTIGATIONAL PLAN

4.1 Overall Study Design

This is a multicenter, open-label, long-term extension study to evaluate the safety and tolerability of oral AERT in patients with spasticity due to MS. Subjects from the double-blind study (Study OSS440-3004) may rollover into this open-label extension study, as well as *de novo* subjects, provided that all inclusion and none of the exclusion criteria are met. Eligible *de novo* subjects will undergo a washout period withdrawing all medications used for anti-spasticity and/or muscle relaxation up to 21 days prior to enrolling in this open-label study. There will be a 9-day titration period, then a 52-week maintenance period, followed by a 2-week taper period. Figure 1 presents the timeline diagram for the study. Figure 2 presents the open-label dosing regimen flowchart, including titration and taper doses, to be used during the study. Once the subject has reached the maintenance dose, they will remain on that dose for approximately 1 year. The maintenance dose will be the highest tolerated dose not exceeding 80 mg per day. Table 1 presents the schedule of assessments, including study visits and weeks, for the study.

4.2 Rationale for Study Design and Dose Selection

Chronic exposure in an open-label extension design is appropriate to evaluate the safety of long-term use of an investigational product. The omission of a control group is appropriate. The subjects will be selected according to predefined entry criteria from the previous Phase 3, randomized, multicenter, double-blind, placebo-controlled study. The open-label study treatment duration of approximately 1 year is adequate for chronic exposure. Nonclinical arbaclofen data from a 3-month rat toxicity study (Study 0460RO24.001) show margins of exposure greater than 1 and adverse effects at exposures up to 10-fold higher than those projected to occur in this Phase 3 study that were not life-threatening, were clinically monitorable, and were reversible, which

supports a dose level of 80 mg. To date, Osmotica has conducted 11 clinical studies (Phases 1 through 3) utilizing AERT in doses up to 80 mg/day in single and divided doses.

The open-label extension study is necessary to obtain safety information about the long-term use of AERT at the highest target dose to treat patients with spasticity due to MS because it is a chronic condition.

5 STUDY POPULATION

It is anticipated that approximately 50% of subjects randomized into the double-blind study (Study OSS440-3004) may rollover into this open-label study. In addition, United States (US) subjects who did not participate in Study OS440-3004 (i.e., *de novo* subjects) may also enroll into the current study provided that all inclusion and none of the exclusion criteria are met. In total, approximately 300 subjects are to be enrolled in order to achieve treatment of at least 100 subjects for 6 months, and 50 subjects at 80 mg/day for at least 1 year; however, the sponsor reserves the right to end this clinical study after a sufficient number of subjects have enrolled to complete the requirement.

5.1 Inclusion Criteria

Male and female subjects will be considered eligible for participation in the study if all the following inclusion criteria are satisfied at Visit 1 (Baseline).

1. Subjects 18 to 65 years of age, inclusive.
2. An established diagnosis per McDonald Criteria ([Polman et al 2011](#)) of MS (either RR or SP course) that manifests a documented history of spasticity for at least 6 months prior to Baseline.
3. Has participated in Study OS440-3004 or is a new US subject (i.e., a *de novo* subject) who fulfills the inclusion/exclusion criteria.
 - a. *De novo* subjects being considered for enrollment must have spasticity due to MS as shown by a TNmAS-MAL score $\geq 2^a$ (Appendix 1)
4. Is willing to continue on open-label treatment with AERT as described in this protocol.
5. If receiving disease-modifying medications (e.g., interferons approved for MS, glatiramer acetate, natalizumab, fingolimod, or mitoxantrone), there must be no change in dose for at least 3 months prior to Baseline, and the subject must be willing to maintain this treatment dose for the duration of the study. If receiving AMPYRA[®] (dalfampridine, fampridine, 4-amino puridine), subject must be at a stable dose for at least 3 months prior to Baseline.
6. Stable regimen for at least 1 month prior to Baseline for all medications and non-pharmacological therapies that are intended to alleviate spasticity.

^a Total numerical score of a limb accounts for the sum of the 3 main joint muscular group scores.

- a. *De novo* subjects being considered for enrollment and taking medications indicated for the treatment of spasticity (i.e., baclofen, benzodiazepines, cannabinoids, carisoprodol, dantrolene, tizanidine, cyclobenzaprine, any neuroleptic, ropinoprole, tolperisone, and clonidine) must wash out from these medications for at most 21 days by Baseline in order to be eligible for study treatment. *De novo* subjects found not to meet this criterion will be withdrawn from the study and will be considered screen failures.
7. Absence of infections, peripheral vascular disease, painful contractures, advanced arthritis, or other conditions that hinder evaluation of joint movement.
8. Creatinine clearance, as calculated by the glomerular filtration rate (GFR) using the Modification of Diet in Renal Disease Study (MDRD) formula,^b of >50 mL/minute.
9. Use of a medically highly effective form of birth control (see [Section 7.8](#)) during the study and for 3 months thereafter for women of child-bearing potential (including female subjects).
10. Willing to sign the informed consent form (ICF).

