5.2 Exclusion Criteria

Subjects who meet any of the following criteria will not qualify for the study.

1. Any concomitant disease or disorder that has symptoms of spasticity or that may influence the subject's level of spasticity.
2. Inability to rate their level of spasticity or distinguish it from other MS symptoms.
3. Use of high dose oral or intravenous methylprednisolone, or equivalent, within 3 months before Baseline.
4. History of allergy to baclofen or any inactive components of the test formulation.
5. Concomitant use of medications that would potentially interfere with the actions of the study medication or outcome variables (Appendix 5).
6. Pregnancy, lactation, or planned pregnancy during the course of the study and for 3 months after the final study visit.
7. Recent history (within past 12 months) of any unstable psychiatric disease (or yes response to questions 1 or 2 on the Columbia Suicide Severity Rating Scale [C-SSRS] at baseline), or current signs and symptoms of significant medical disorders such as severe, progressive,

^b GFR Calculator:

$GFR \text{ (mL/min/1.73 m}^2\text{)} = 175 \times (\text{Scr (mg/dL)})^{-1.154} \times (\text{Age (years)})^{-0.203} \times (0.742 \text{ if female}) \times (1.212 \text{ if African American})$ (conventional units)

$GFR \text{ (mL/min/1.73 m}^2\text{)} = 175 \times (\text{Scr } (\mu\text{mol/L})/88.4)^{-1.154} \times (\text{Age (years)})^{-0.203} \times (0.742 \text{ if female}) \times (1.212 \text{ if African American})$ (SI units)

or uncontrolled pulmonary, cardiac, gastrointestinal, hepatic, renal, genitourinary, hematological, endocrine, immunologic, or neurological disease.

8. History of epilepsy.
9. Current significant cognitive deficit, severe or untreated anxiety, severe or untreated depression.
10. Subjects with abnormal micturition that requires indwelling or intermittent catheterization or with lower urinary tract symptoms (LUTS) that result in a score >26 in the Baseline Urinary Symptom Profile – USP[®] (USP) questionnaire (Appendix 6). Subjects who are proficient in self-catheterization may be included in the study at the investigator's discretion.
11. Current malignancy or history of malignancy that has not been in remission for more than 5 years, except effectively treated basal cell skin carcinoma.
12. Subject has clinically significant abnormal laboratory values, in the opinion of the investigator at Screening (at Visit 6 for rollover subjects).

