7.7 Prior and Concomitant Therapy

The inclusion and exclusion criteria (Section 5.1 and 5.2, respectively) provide details on prohibited medications and food and the permitted duration since their last use prior to Baseline and/or study drug administration. For *de novo* subjects, all medications taken within 30 days before Baseline are to be recorded in the electronic case report form (eCRF). Eligible *de novo* subjects will undergo an up to 21-day washout period (no drug onboard) for withdrawal of all medications used for anti-spasticity and/or muscle relaxation prior to Baseline (see Inclusion Criterion 6). Any subject will be ineligible for the current open-label study if they are concomitantly using any of the medications listed in Appendix 5 (see Exclusion Criterion 5).

Table 3 presents the half-life, taper period, and washout period for specific anti-spasticity and/or muscle relaxation medications. Tapering of an existing anti-spasticity drug depends on the dose of the drug and other conditions. The investigator should use medical judgment to safely taper the dose. Under most conditions, the taper should take no more than 2 weeks. For anti-spasticity medications not shown in Table 3, please contact the medical monitor for discussions of the washout period.

Table 3: Taper and Washout Periods for Specific Anti-spasticity and/or Muscle Relaxation Medications, Study OS440-3005

Drug	Half-Life (hours)	Taper Period	Washout Period
Baclofen	3 to 5	3 to 14 days	1 day
Clonidine	12 to 16	3 to 14 days	3 days
Dantrolene	8 to 9	3 to 14 days	2 days
Gabapentin	5 to 7	3 to 14 days	2 days
Zanaflex	3	3 to 14 days	1 day
Diazepam	100	3 to 14 days	3 weeks

Other than anti-spasticity medications, all conventional medications regularly used for the treatment of MS and all non-pharmacological therapies (intended to alleviate spasticity, e.g., physiotherapy) are allowed provided they have been taken/administered for at least 1 month prior to enrollment and no dose adjustments are expected for the duration of this study.

Changes in either the dose or frequency of concomitant medications taken for the treatment of MS should not be made for the duration of this study. In the event a dose adjustment is needed for a concomitant medication, the investigator will contact the Sponsor to determine if the subject may remain in the study or needs to be withdrawn.

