Appendix 5. Prohibited Concomitant Medication List

[figure not shown]
- Aminoglycoside antibiotics
- Baclofen
- Benzodiazepines for anti-spastic indication
- Botulinum toxin therapy of any serotype
- Cannabinoids
- Carisoprodol
- Chlormezanone
- Curariform drugs
- Dalfampridine
- Dantrolene
- Gabapentin for anti-spasticity indication
- Meprobamate
- Methocarbamol
- Neuroleptics
- Orphenadrine
- Cyclobenzaprine
- Tizanidine
- Tolperisone

[figure not shown]

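### Inclusion 5 anticipates stable dalfampridine users, but Exclusion 5, Section 7.7 and Appendix 5 bar them, so the intended eligibility rule is unclear

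*Protocol*

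**What the plan says.** Four places in the current protocol bear on a subject who is taking dalfampridine.

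- **Section 5.1, Inclusion 5.** After dealing with disease-modifying drugs, the criterion turns to subjects receiving dalfampridine and requires that the "subject must be at a stable dose for at least 3 months prior to Baseline".
- **Section 5.2, Exclusion 5.** This excludes concomitant drugs that could interfere with the study drug or with the outcome measures, and points to Appendix 5 for the list.
- **Appendix 5.** Under the title "Prohibited Concomitant Medication List" there is the one-word entry "Dalfampridine".
- **Section 7.7.** This turns the list into an explicit eligibility rule: "Any subject will be ineligible for the current open-label study if they are concomitantly using any of the medications listed in Appendix 5".

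Section 7.7 also contains a general allowance. Apart from anti-spasticity drugs, it permits "all conventional medications regularly used for the treatment of MS" if taken for at least 1 month before enrolment with no dose change expected.

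The SAP does not mention dalfampridine. SAP Section 8.2 plans a listing of all protocol deviations and a summary table by classification.

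**The concern.** A stability condition written for users of a named drug has an obvious purpose: it says on what terms they may come in. An investigator who checks Inclusion 5 finds such terms for dalfampridine, with no pointer to Appendix 5. An investigator who checks Appendix 5 or Section 7.7 finds a flat prohibition, with no pointer to Inclusion 5.

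Two things are at stake in a multicenter study. The first is consistent enrolment: the same candidate may be accepted at one site and refused at another, and the rule reaches rollover and de novo subjects alike. The second is consistent reporting: whether an enrolled user counts as a deviation may depend on which section the site or monitor applied, and SAP Section 8.2 tabulates the result.

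There is a lesser point of interpretation. Exclusion 5 gives possible interference with the outcomes as its reason for excluding drugs. SAP Sections 7.2.1 and 7.2.2 plan no covariates and no subgroups, so no planned summary would separate users from non-users.

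**Working it through.** No arithmetic applies. The check is whether any reading of the current text lets all four passages operate together.

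1. **Apply the combination rule.** Protocol Sections 4.1, 5 and 7.4 require every inclusion criterion and no exclusion criterion to be met. Take a subject on dalfampridine whose dose has been unchanged for more than 3 months:

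| Provision | Result for this subject |
|---|---|
| Inclusion 5 | Condition met |
| Exclusion 5 with Appendix 5 | Excluded |
| Section 7.7, Appendix 5 sentence | Ineligible |
| Both sets of criteria combined | Ineligible |

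 A user with an unstable dose fails Inclusion 5 as well. Every current user is therefore out, whatever the dose history, and the dalfampridine clause never changes an outcome.

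2. **Is the Appendix 5 entry limited in some way?** No. The appendix adds a qualifier where one is meant, as in "Gabapentin for anti-spasticity indication", and it does the same for benzodiazepines. The dalfampridine entry has no qualifier of dose, stability or indication.

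3. **Could the intent be a stable dose followed by withdrawal before Baseline?** The text does not support this. Dalfampridine is absent from the washout list in Inclusion 6a and from the taper and washout periods in Table 3. A washout before Baseline would also conflict with a dose that must be stable for the 3 months leading up to Baseline. Inclusion 5 does not ask dalfampridine users to keep their dose during the study, as it does for disease-modifying drugs, but no passage tells them to stop.

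4. **Does the general allowance in Section 7.7 settle it?** No. If dalfampridine is read as a conventional MS medication, the allowance gives a third answer, with a 1-month period in place of 3 months. It still collides with the Appendix 5 sentence in the same section.

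5. **Is one of the passages superseded?** No. All four are current text, and the summary of changes in Appendix 8 does not mention dalfampridine.

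6. **How many subjects are involved?** The count would be the number enrolled (about 300 planned, Section 11.3) times the share using dalfampridine at entry. The documents do not give that share for rollover or de novo subjects, so the count cannot be calculated.

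**The case against.** The strongest reply is that the documents already yield an answer. Inclusion 5 states a necessary condition and does not declare users eligible. Section 5.2 says that meeting any exclusion criterion disqualifies, and Section 7.7 says the same of Appendix 5 drugs. Applied literally, a current user is ineligible and no rule is broken.

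That reply stands, and it rules out several stronger readings that a reader might infer:

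- *That eligibility is undecidable, or that the rules cannot both be followed.* They can, at the price of an Inclusion 5 clause that does nothing.
- *That every enrolled user is at once eligible and a deviation, making the deviation table arbitrary.* Under the combination rule such a subject failed Exclusion 5 and is a deviation. The risk is uneven recording.
- *That sites will differ.* The documents support only that they may.
- *That the safety estimates lose their target population.* The Safety population is defined by at least one dose and at least one post-dose visit (Protocol Section 11.2, SAP Section 7.1.2), so an enrolled subject's membership does not depend on this criterion.

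It is also fair to say that users can already be identified. Medications are recorded in the eCRF (Protocol Section 7.7) and listed (Protocol Section 11.5). SAP Section 8.5 summarises concomitant medications by ATC level 4 and preferred term, and SAP Section 7.4.1 lists all collected data. A separate listing of dalfampridine users would add little.

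The reply does not explain why the protocol carries a drug-specific entry condition that can never operate. A sentence with no effect is evidence that one of the passages does not say what was meant, and the text does not show which.

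**Conclusion.** The point holds as an internal inconsistency in an operative eligibility rule. The literal combined reading excludes current users, but it empties a specific clause of Inclusion 5, so the intended rule is unclear. The practical exposure is possible differences between sites in enrolment and in the recording of deviations.

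The size is unknown, and any count of affected subjects would be a guess. No test or sample-size figure changes: SAP Section 7.4.1 plans no statistical tests, and Protocol Section 11.3 gives no statistical rationale for the number of subjects. The conclusion rests on the wording of the current protocol alone and needs no assumption about how often the drug is used. It should be corrected, but it does not undermine the planned analysis.

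**What to change.** Reconcile Inclusion 5, Exclusion 5, Appendix 5 and Section 7.7 so that one rule on dalfampridine applies at every site. Which rule is for the sponsor to decide; none is proposed here. The reconciled text should also make clear whether the general allowance for MS medications in Section 7.7 covers the drug. Appendix 8 describes the latest amendment as specific to the United States, so any protocol version in force elsewhere should be checked for the same wording.

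For SAP Section 8.2, classify dalfampridine users already enrolled in one consistent way in the deviation summary, under the reconciled rule. No new listing or analysis is needed.

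The wording change is short, but it alters eligibility criteria. It therefore needs a protocol amendment with sponsor and IRB/IEC approval (Protocol Sections 12.2 and 13.2), plus at most one sentence in the SAP.

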6.2 Baseline – Visit 6 (Final Visit) of Study OS440-3004 (Week 0)

For *de novo* subjects, the following assessments and procedures will be performed at the Baseline visit: assign enrollment number, vital signs, urine pregnancy test, C-SSRS, TNmAS-MAL, PGIC,

USP, dispensing of study medication, recording of AEs and concomitant medications, and scheduling/confirmation of the next study visit.

For Study OS440-3004 subjects willing to continue into this study, Baseline for this study will be conducted at the same time as Visit 6/Day 92 (Final Visit) of Study OS440-3004. All assessments performed at Visit 6/Day 92 (Final Visit) of Study OS440-3004 should not be repeated but should be recorded as the same assessments at Baseline for this study.

At Baseline, the investigator will fully explain to the subject the objectives, characteristics, and procedures for the open-label study. Baseline assessments/procedures will include the following:

- Obtain a signed and dated ICF from each subject prior to any study-specific procedures being conducted ([Section 13.3](#)).
- Assess eligibility according to the inclusion ([Section 5.1](#)) and exclusion criteria ([Section 5.2](#)).
- Assignment of an enrollment number ([Section 7.4](#)).
- Record demographic data, including age, sex, race, and ethnicity.
- Record medical and surgical history ([Section 9.1](#)).
- Record physical examination results ([Section 9.3](#)).
- Record weight and height ([Section 9.4](#)).
- Record vital sign measurements, including blood pressure (BP), heart rate, respiratory rate, and body temperature ([Section 9.2](#)).
- Collect blood and urine samples for hematology, serum chemistry, and urinalysis ([Section 9.5](#)). Subject should be fasting if possible.
- Perform a standard 12-lead electrocardiogram (ECG) ([Section 9.6.1](#)).
- Because contraception is required throughout the study for both males and females, the use of an acceptable method throughout the study will be discussed with all subjects ([Section 7.8](#)).
- Collect a urine sample for pregnancy testing for women of childbearing potential ([Section 7.8](#)).
- Administer the Columbia–Suicide Severity Rating Scale (C-SSRS) ([Section 9.6.3](#)).
- Perform the TNmAS-MAL assessment ([Section 8.2](#)).
- Administer the EDSS assessment ([Section 8.3](#)).
- Administer the PGIC questionnaire ([Section 8.1](#)).
- Administer the USP questionnaire ([Section 9.6.2](#)).

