7.4 Method of Assignment of Study Drug

[figure not shown]
This is an open-label study and all subjects will begin treatment with AERT at 40 mg per day (20 mg BID) for 3 days, then increase to 60 mg per day (20 mg in the morning and 2 x 20 mg in the evening) for 3 days, and then increase to 80 mg per day (2 x 20 mg BID). Once the subject has reached the maintenance dose, they will remain on that dose for approximately 1 year. The maintenance dose will be the highest tolerated dose, not exceeding 80 mg per day. Subject will be allowed to taper the 80-mg/day dose for issues of tolerability on at most three occasions. If tolerability issues persist, the subject will be required to discontinue from the study.

After Baseline procedures have been completed, authorized site personnel will acknowledge that the applicable subject met all the specified inclusion criteria ([Section 5.1](#)) and none of the exclusion criteria ([Section 5.2](#)) and an enrollment number will be sequentially assigned.

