7.8 Use of Contraception and Pregnancy Testing

Prior to study enrollment, females of childbearing potential and female partners of male subjects must be advised of the importance of avoiding pregnancy during study participation and the potential risk factors for an unintentional pregnancy. Females of childbearing potential include any female who has experienced menarche and who has not undergone successful surgical sterilization (hysterectomy, bilateral tubal ligation/occlusion, or bilateral oophorectomy) or is not postmenopausal (defined as amenorrhea >12 consecutive months). *De novo* premenopausal women of childbearing potential must have a negative serum pregnancy test within 21 days before Baseline and all enrolled subjects, if they are sexually active or become sexually active during the study, must use an effective method of birth control such as those listed below during the course of the study. Urine pregnancy testing will be done at Visits 1 through 8.

The following is not an all-inclusive list; the subject must discuss with the investigator the most appropriate form of birth control:

- Hormonal methods
 - Oral contraceptives
 - Implant
 - Injection
 - Transdermal patch

- Intravaginal ring
- Intrauterine device (hormonal or non-hormonal)
- Barrier methods
 - Condom (male or female) with spermicide
 - Diaphragm with spermicide
- Complete abstinence

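### Sections 7.8 and 6.2 give women a weaker and shorter contraception rule than Inclusion Criterion 9, which itself refers the reader to 7.8

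*Protocol*

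**What the plan says.** **Eligibility.** Inclusion Criterion 9 (Protocol 5.1) requires "Use of a medically highly effective form of birth control", gives a cross-reference to Section 7.8, and sets the period and the people covered: "during the study and for 3 months thereafter for women of child-bearing potential (including female subjects"). Exclusion Criterion 6 (Protocol 5.2) uses the same window, excluding "planned pregnancy during the course of the study and for 3 months after the final study visit".

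**Counselling.** Under Section 7.8, enrolled subjects who are or become sexually active "must use an effective method of birth control such as those listed below during the course of the study". The list of methods opens with "The following is not an all-inclusive list; the subject must discuss with the investigator the most appropriate form of birth control". Section 6.2 says contraception is required of both sexes while the study lasts and that "the use of an acceptable method throughout the study will be discussed with all subjects", again referring to 7.8.

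**Enrollment check.** Under Section 7.4, once Baseline procedures are complete, "authorized site personnel will acknowledge that the applicable subject met all the specified inclusion criteria", and an enrollment number is then assigned.

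**Partner pregnancy.** Section 12.4 withdraws a subject whose partner becomes pregnant during the study, follows that subject to the end of the pregnancy, and cites Section 9.7.5. Section 9.7.5 requires that female partners of male subjects be advised before enrollment, and that the consent form record the discussion. Its instruction to contact the investigator is addressed to female subjects of childbearing potential.

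**The concern.** Inclusion 9 sends the site to 7.8 for detail, and 7.8 then states a different rule. The required standard drops from highly effective to effective, and the 3 months after the study disappear. Section 6.2 uses a third term, acceptable, and also stops at the end of the study. Nothing in the text supplied defines highly effective or says which listed methods reach it, yet site personnel must confirm that the criterion is met.

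The phrase in brackets in Inclusion 9 adds to the difficulty. Female subjects are already the women the criterion covers, so as printed it does not make clear who else, if anyone, is bound.

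What is at stake is the advice a woman receives about how well and how long to avoid pregnancy after exposure to the drug. A lesser matter is whether the site would learn of a partner's pregnancy in time to apply Section 12.4.

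**Working it through.** The plan gives no figure to reproduce. The check is a comparison of texts and one piece of calendar arithmetic.

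**Texts side by side**

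| Place | Who is covered | Standard of method | Period |
|---|---|---|---|
| Inclusion 9 (5.1) | Women of child-bearing potential | Highly effective | Study plus 3 months |
| Exclusion 6 (5.2) | Subjects planning pregnancy | None stated | Study plus 3 months after final visit |
| Section 7.8 | All enrolled subjects, if sexually active | Effective | Study only |
| Section 6.2 | Men and women | Acceptable | Study only |

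The two eligibility criteria agree on duration. Sections 7.8 and 6.2 are the outliers. Section 7.8 is weaker in standard and shorter in time, but wider in whom it covers, because it includes men.

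**Length of the gap**

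Inputs: the taper runs from Week 54 to Week 56 (Protocol 7.5) and Visit 8 is at Week 60 (Protocol Table 1). I take 3 months as about 13 weeks, treat the study as ending for the subject at the Final Visit, and ignore visit windows of 3 to 5 days.

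For a completer who tapers:
- Section 7.8 read alone: 60 − 56 = 4 weeks after the last dose.
- Inclusion 9: 60 + 13 = Week 73, and 73 − 56 = 17 weeks after the last dose.
- Difference: 17 − 4 = 13 weeks.

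The difference does not depend on when dosing stops. With Final Visit at week V and last dose at week L, it is (V + 13 − L) − (V − L) = 13 weeks. It therefore also holds for early withdrawals, for whom the protocol fixes no interval between last dose and Final Visit.

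**Partner pregnancy**

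Section 12.4 supplies the action (withdraw and follow) and Section 9.7.5 supplies the advice before enrollment. Between them there is no sentence asking a male subject to tell the site that his partner is pregnant.

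**The case against.** The strongest reply is that Inclusion 9 governs. It states its own duration, and its cross-reference follows the words on the form of birth control, so it can be read as pointing to 7.8 for methods only. Section 6.2 lists the check against all criteria beside the contraception discussion, and Section 7.4 requires confirmation of every criterion. This stands: a reader might infer that a woman could be enrolled under the weaker rule, and the documents do not support that. What remains is that the counselling text contradicts the criterion.

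Three further inferences are tempting but not supported.

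- *That listed barrier methods fail Inclusion 9.* Section 7.8 includes, for example, "Condom (male or female) with spermicide". The documents never define highly effective, so whether this qualifies cannot be settled from them. The list is also open and leaves the choice to discussion with the investigator.
- *That the protocol ignores partners.* Section 9.7.5 requires partners to be advised and Section 12.4 states what follows a partner's pregnancy. Only the instruction to report is missing.
- *That pregnancies in the 3 months after the study go unreported in breach of the plan.* The 3 months are a window for contraception and planned pregnancy. Nothing in the plan makes them a reporting window. Section 9.7.3 also names an exposure-during-pregnancy form, although its scope is not stated. Extending reporting is the sponsor's option.

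**Conclusion.** The conflict is real and lies in the current operative text. For women, Sections 7.8 and 6.2 state a lower standard than Inclusion 9 and a period about 13 weeks shorter than Inclusion 9 and Exclusion 6.

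Severity is minor. Women are already bound to the 3 months at eligibility, planned dosing ends by Week 56 for completers, and a urine pregnancy test is scheduled at Week 60. The 13 weeks measure the gap in wording and are not an estimate of risk.

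The conclusion assumes that a site could counsel from 7.8 or 6.2 without returning to 5.1. It also rests on the protocol alone: the consent form is not available here and may already state the full rule. The missing instruction to male subjects is secondary and carries the same caveat.

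**What to change.** 1. In Sections 7.8 and 6.2, state for women of child-bearing potential the Inclusion 9 standard and the full period, meaning the study plus 3 months. Say in 7.8 which listed methods meet that standard. The sponsor decides which do.
2. Keep the existing during-study rule for male subjects as a separate sentence. The 7.8 sentence covers all enrolled subjects, so pasting the Inclusion 9 wording into it would extend the higher standard and the 3 months to men. That should happen only if the sponsor chooses it.
3. In Inclusion 9, replace the bracketed phrase with a plain statement of who is bound.
4. In Section 9.7.5, add one instruction that male subjects report a partner's pregnancy to the investigator, so that Section 12.4 can be applied.
5. Check that the consent form says the same.

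The cost is rewording the protocol, and the consent form where needed, with sponsor and IRB/IEC approval under Section 12.2. There may be a few partner pregnancies to record and follow. No scheduled visit, test or analysis is added.
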